Our unique combination of pediatric and adult endocrinology skills, laboratory expertise in insulin signaling, and clinical research experience in insulin sensitivity testing in obese youth make us perfectly poised to address these hypotheses. In addition, the use of a longitudinal study design will allow us to examine differences in percent body fat, body fat distribution and changes in BMI over time in the observational arm of the study. It also allows to examine whether treatment of obese children during this time can have beneficial effects on insulin sensitivity and secretion in the treatment arm. Enhancing our understanding of longitudinal changes of insulin sensitivity in obese adolescents and the response to metformin will help us identify potential interventions aimed at the prevention of T2DM.

The studies in this proposal will test the following hypotheses:

HYPOTHESES:

- 1. Obese adolescents, unlike normal weight controls, fail to improve insulin sensitivity at the end of puberty.**
- 2. Treatment of obese adolescents with metformin during puberty will help these individuals result in sustained improvement in insulin sensitivity at the end of puberty, decrease compensatory hyperinsulinemia, and preserve insulin secretion, thereby improving their disposition index (DI).**

To test these hypotheses, we propose to address the following Specific Aims:

SPECIFIC AIM 1 (Observational Arm):

- 1. To compare longitudinal changes in insulin sensitivity and secretion and their correlates in obese and normal weight adolescents during puberty.**
 - a. To compare changes in insulin sensitivity and secretion as measured by frequently sampled intravenous glucose tolerance test (IVGTT) from early puberty to puberty completion between obese and normal weight adolescents.**

- b. To compare changes in body composition, fat distribution, and inflammatory markers over time between these groups.**

Under this Specific Aim, insulin sensitivity and secretion will be measured by frequently sampled IVGTT in early puberty and at puberty completion in obese and normal weight adolescents. Changes in insulin sensitivity will be correlated with changes in inflammatory markers in all participants and body composition in a subset of these participants.

[figure not shown]
SPECIFIC AIM 2 (Treatment Arm):

- 2. To compare changes in insulin sensitivity and secretion and their correlates, in obese adolescents treated with metformin or placebo during puberty.**

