Metformin acts by decreasing endogenous hepatic glucose production, thereby lowering insulin requirements (28). Several studies of metformin have been performed on insulin resistant children, with variable outcomes. Three of these studies were controlled, randomized, double-blind and specifically targeted obese, insulin resistant adolescents with normal glucose homeostasis (29-31). Srinivasan et al treated 28 adolescents aged 9-18 years in a one-year double-blind crossover trial (6 mos. metformin at a dose of 1g BID, 6 mos. placebo). Fasting insulin, glucose and BMI standard deviation scores (SDS) were significantly decreased after the treatment period compared with the placebo period. However, insulin sensitivity, insulin secretion and DI, as measured by Bergman's minimal model method, did not change (31). Similarly, 32 obese adolescents aged 12 to 19 years with a family history of T2DM had a significant decrease in BMI SDS, fasting glucose and fasting insulin after 6 months of 500 mg metformin BID compared with placebo (29). Again there was no change in insulin sensitivity as measured by the minimal model. Data on insulin secretion and DI were not reported. Finally, Kay et al assessed effects of 850 mg metformin BID on obesity and insulin sensitivity in 24 obese adolescents in a randomized, placebo controlled trial. Those in the treatment group had greater weight and body fat loss than the controls and had a decrease in area under the curve (AUC) for insulin (as measured by OGTT), but no change in glucose AUC. They also had a significant decrease in triglycerides. Insulin secretion was not measured. In all of these studies the treatment period was relatively short and none of them targeted the most resistant time of puberty. Furthermore, the Freemark study used a metformin dose that is approximately one half the standard dose used to treat diabetes or PCOS.

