Ibanez et al, in Spain, have used metformin in multiple clinical trials of female children and adolescents with premature pubarche (PP) associated with a history of low birth weight. Being small for gestational age is thought to predispose certain infants to developing decreased insulin sensitivity later in life. The girls participating in these studies had evidence for reduced insulin sensitivity, as assessed by elevated insulin levels, but were not obese (32-37). Treatment length and doses were variable, as well as timing of treatment in relation to puberty. Furthermore, none of these trials was randomized or double-blinded, and measures of insulin sensitivity were not consistent. Regardless, treatment with metformin in all these trials resulted in improvements in insulin levels and triglycerides and in several, a reduction in BMI. Most interestingly, one trial showed a persistence of beneficial effects 12-18 months after the metformin was stopped (32). In this trial, 22 girls with a history of PP and low birth weight were randomized to receive metformin treatment (850 mg daily) or no treatment within one year of starting breast development and treated for 36 months (32;35). At the end of the treatment period, change in BMI, IR as measured by HOMA, triglycerides, abdominal fat mass, leptin and total fat mass were all improved in the metformin group compared with the untreated group. Furthermore, these differences between the groups persisted for 12 months after the treatment was stopped. Despite some design flaws, this study suggests that short-term treatment with metformin during puberty can result in sustained metabolic benefit in adolescents at increased risk for developing T2DM.

Inflammatory markers and cytokines: relation to IR

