significant difference in weight loss among subjects receiving metformin or placebo. However, 11 (23%) subjects on metformin had a BMI decrease of 5% or more, while no subjects on placebo were able to attain this degree of weight loss. Of 11 subjects decreasing BMI by 5%, 82% were female. 45% were Hispanic, 27% Black, 18% Caucasian and 9% Asian.

All subjects had elevated fasting insulin levels at baseline, with an average level of 39.8 μ IU/ml. At the end of 6 months, the metformin group had a significant decrease in fasting insulin compared with the placebo group ($-9.8 \pm 3.4 \mu$ IU/ml vs. $-3.1 \pm 2.6 \mu$ IU/ml, $p < 0.05$). Furthermore, the metformin group had significantly decreased fasting triglycerides at the 6 month follow-up compared with the placebo group (-26.2 vs. -0.2 , $p < 0.05$) (unpublished data) and triglycerides were shown to be a significant predictor of IGT in this cohort (53). Finally, the metformin group had a significantly improved fatty liver score, as measured by ultrasound (mean change -0.4 ± 0.1 vs. $+0.25 \pm 0.28$, $p < 0.05$) (54).

Subjects on metformin were slightly less likely to have good pill compliance (68% vs. 78% on placebo). 29% of subjects on metformin reported side effects: nausea or vomiting (14%), diarrhea (14%), or abdominal pain (11%) vs. 22% of subjects on placebo: nausea (11%) or diarrhea (11%) but no subjects required dose reductions. There were no significant differences in attrition between the groups.

Thus, metformin may be a candidate for primary prevention of T2DM in high-risk adolescents. Extended release metformin is available as a generic medication; it is relatively inexpensive and accessible. Furthermore, this trial shows that long-term treatment with metformin is safe and feasible in our adolescent population.

2. Studies of Intramyocellular lipid deposition in relation to Insulin Sensitivity

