β -cell function will be preserved. This would make puberty a potential treatment period to target prevention of T2DM.

DESIGN

Participants:

1. 104 Obese participants:
 - a.) BMI \geq 95th percentile
 - b.) Tanner stage II – III at baseline
 - c.) Age \geq 9 years
 - d.) Absence of impaired glucose tolerance (IGT), impaired fasting glucose (IFG) or T2DM, as determined by oral glucose tolerance test (OGTT)

Exclusion criteria:

See Specific Aim 1

Approach:

All obese subjects who are recruited will be randomized after Study Visit 1 to receive metformin or placebo. The 52 participants randomized to the placebo group will then also serve as the obese subjects for the longitudinal observational studies of Specific Aim 1 (Please see Fig 2 for further clarification). In other words, 52 obese participants will be included in both Specific Aims 1 and 2, in order to minimize the total number of participants needed. Randomization will be stratified by: 1) Family history in a first degree relative with T2DM or no family history and 2) BMI between the 95th and 99th percentile or BMI greater than the 99th percentile. The extended release metformin will be started at 500 mg daily for one week and then increased by 500 mg a week until the target dose of 2000 mg a day is attained. The extended release preparation allows patients to take the medication once a day to promote improved adherence and is better tolerated. All obese participants will receive standard lifestyle counseling, focusing primarily on dietary improvements and increased physical activity. The total treatment period will be two years to include, on average, the most resistant stages of puberty. In order to monitor metformin compliance closely, the participants will come in for monthly pill-counts. In addition, each participant will be provided with a pill dispenser and a calendar to record each dose that is taken to assist with and track compliance. Furthermore, parents will be encouraged to remind the participant to take his/her medication. Participants will be given a point each time they bring in their pill bottle, whether or not they have been compliant, and will be eligible for an extra gift card for every 6 points they obtain. Our group has extensive experience in maintaining metformin compliance in this population (52). Tanner staging, anthropometric measurements and lifestyle counseling will also be performed at quarterly visits.

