Sample size calculation: A recruitment goal of 52 participants per group has been set (normal weight controls, obese controls, obese on metformin—a total of 156 participants). Assuming a 30% drop-out rate, this will give a final sample size of 30 per group. Power was run in PASS (NCSS Software; Kayesville, UT) and was calculated using a one-way ANOVA with a two-sided significance level of 0.05. Variability of the estimates was based on data available in an article by Buchanan et al. (57) in which IVGTT insulin sensitivity was measured in high-risk Hispanic women at baseline and 3 months for a placebo (n=109) and a troglitazone group (n=108). The 3-month change was -0.17 and 1.16 min^{-1} per $\mu\text{U}/\text{ml} \times 10^{-4}$, for the placebo and treatment groups, respectively. Assuming a correlation of 0.5, the estimated overall standard deviation of the 3-month change for both the placebo and treatment groups was 1.85 min^{-1} per $\mu\text{U}/\text{ml} \times 10^{-4}$. For this study, we assume similar variability and expect the 2-year change for the obese control and metformin groups to also be similar to those seen in the Buchanan et al. groups. The 2-year insulin sensitivity change in normal controls is expected to be similar to the change seen in Ball et al. (11) for 46 white adolescents from Tanner II / Tanner III to Tanner V, which was 1.6 min^{-1} per $\mu\text{U}/\text{ml} \times 10^{-4}$. Therefore, with a standard deviation of 1.85 and expected 2-year changes of 1.16, -0.17 and 1.6 for the metformin, obese control and normal control groups, respectively, a sample size of 30 per group achieves 93% power to detect an overall difference between the groups.

Statistical analysis: All analyses will assume a two-sided test of hypothesis with an overall significance level of 0.05 and will be performed in either SAS v9.1.3 or above (SAS Institute, Inc., Cary NC) or Splus v7.0 or above (Insightful Corp, Seattle WA).

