Simple descriptive statistics will be calculated for all variables (mean, median, standard deviation, minimum and maximum values for continuous variables; number and percentage of subjects for categorical variables). Linear regression will be used to compare 2-year change in insulin sensitivity, insulin secretion, and DI between groups for Specific Aims 1 and 2 (normal controls vs. obese controls and obese treated vs. obese controls). Potential confounders such as sex, 2-year change in percent body fat and 2-year change in BMI will be included in each model. In order to determine if the benefit of treatment persists beyond stopping treatment, the above analysis will be repeated on the change from baseline to 6 months post-treatment for the obese treated and obese control groups only. The mean change in each outcome from treatment stoppage to 6 months post treatment will also be calculated with 95% confidence intervals (CI) in order to assess maintenance of the level of each outcome. Although we are not powered for equivalence (to test the hypothesis that the 6-month change is equal to zero), the precision of the estimate and whether the difference is *clinically* significant will be evident from the 95% CI. A CTRC biostatistician will be available to consult on all matters of statistics.

Potential Difficulties and Limitations/Alternatives

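### The metformin versus placebo regressions adjust for 2-year change in BMI and body fat, both measured after randomisation, so no planned model estimates the total treatment effect in Hypothesis 2

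*Combined protocol and SAP*

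**What the plan says.** Section D, Statistical analysis, plans linear regressions of 2-year change in insulin sensitivity, insulin secretion and disposition index (DI) for two contrasts: normal controls versus obese controls (Aim 1), and obese treated versus obese controls (Aim 2). One covariate sentence serves both: "Potential confounders such as sex, 2-year change in percent body fat and 2-year change in BMI will be included in each model".

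To assess persistence after treatment stops, "the above analysis will be repeated on the change from baseline to 6 months post-treatment", in the two obese groups only.

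On timing, the Approach under Specific Aim 2 says: "All obese subjects who are recruited will be randomized after Study Visit 1 to receive metformin or placebo".

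On the question to be answered, Hypothesis 2 reads in part: "Treatment of obese adolescents with metformin during puberty will help these individuals result in sustained improvement in insulin sensitivity at the end of puberty". It goes on to hyperinsulinaemia, secretion and DI, and does not restrict the claim to effects independent of weight or fat. The sample size section uses "expected 2-year changes of 1.16, -0.17 and 1.6 for the metformin, obese control and normal control groups", again without conditioning on adiposity.

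Specific Aim 2, item b, makes change in body composition and fat distribution an outcome of the same randomised comparison.

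**The concern.** A confounder of a treatment comparison must influence who receives treatment. Changes in BMI and percent body fat after randomisation cannot do that, but treatment may influence them. The protocol's own background says so. Of one randomised trial it reports: "Those in the treatment group had greater weight and body fat loss than the controls". Of a series of trials in girls with premature pubarche it reports: "treatment with metformin in all these trials resulted in improvements in insulin levels and triglycerides and in several, a reduction in BMI". Of the group's own earlier trial it reports: "11 (23%) subjects on metformin had a BMI decrease of 5% or more", against none on placebo.

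Two things follow if metformin does shift adiposity. First, any part of its effect on insulin sensitivity that acts through adiposity is taken out of the treatment coefficient. Second, conditioning on adiposity change links treatment to other causes that adiposity change shares with insulin-sensitivity change, such as diet and activity. The coefficient can then be biased even as an estimate of the direct effect.

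This is the only planned between-group test of Hypothesis 2, and it applies to all three outcomes at both time points. A null result could not be told apart from a benefit that had been adjusted away.

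**Working it through.** **1. Is there another planned analysis of the total effect?** Three candidates were checked.
- The one-way ANOVA in the sample size section has no covariates, but it is used only for power.
- The mean change from treatment stop to 6 months, with its 95% CI, is not described as a between-group comparison.
- The 6-month persistence analysis repeats the adjusted models.

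The plan contains no model without the change covariates, no direct-effect estimand and no mediation rationale.

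**2. Inputs (sample size section).** Expected changes are 1.16 (metformin), -0.17 (obese control) and 1.6 (normal control). SD is 1.85, with 30 per group and two-sided alpha 0.05.

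**3. Reproduce the plan's figure.** The grand mean is (1.16 - 0.17 + 1.6)/3 = 0.863. The noncentrality is 30 × [(0.297)² + (-1.033)² + (0.737)²] / 1.85² = 14.9. With 2 and 87 degrees of freedom, power is 93.45%, which agrees with the stated 93%.

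**4. Metformin versus placebo without the change covariates.** The difference is 1.16 - (-0.17) = 1.33. Its standard error is 1.85 × √(2/30) = 0.478, so the noncentrality is 1.33/0.478 = 2.78. Noncentral-t power with 58 degrees of freedom is 78.2%.

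**5. What the adjusted model targets.** The documents give no mediated share, so s is an assumption. Let m be adiposity change in within-arm SD units, signed so that higher values favour insulin sensitivity:

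- m = a·t + N(0,1)
- y = (1 - s)·1.33·t + b·m + e, with within-arm SD of y equal to 1.85
- b = 1.85·√R², where R² is the within-arm outcome variance explained by adiposity change
- a = s·1.33/b, the adiposity shift that the share implies

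The adjusted coefficient is 1.33 × (1 - s): 1.33, 1.20, 1.00 and 0.67 for s = 0, 10%, 25% and 50%. Its standard error is 1.85·√(1 - R²)·√(2/30)·√(1 + a²/4).

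Simulated power at 30 per arm (5,000 trials per setting; ranges span one covariate and two correlated covariates), with the implied shift a in brackets:

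| Mediated share | Target | R² = 0.10 | R² = 0.25 | R² = 0.50 |
|---|---|---|---|---|
| 0% | 1.33 | 81–82% (0) | 88–89% (0) | 97% (0) |
| 10% | 1.20 | 72% (0.23 SD) | 80–81% (0.14 SD) | 92% (0.10 SD) |
| 25% | 1.00 | 53–54% (0.57 SD) | 63–64% (0.36 SD) | 80–82% (0.25 SD) |
| 50% | 0.67 | 24% (1.14 SD) | 29–31% (0.72 SD) | 45–46% (0.51 SD) |

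The standard-error formula above gives power within about 2 points of every cell. Worked example for s = 50%, R² = 0.10: b = 0.585, a = 0.665/0.585 = 1.14, SE = 0.521, noncentrality 0.665/0.521 = 1.28, power 24%.

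Six of the twelve cells are at or above the 78% of step 4: all three at 0%, two at 10% and one at 25%. The lowest cells need large adiposity shifts. The power figures also refer to different targets, so the table shows how far the analysis moves from the stated question. It is not a net loss of power.

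**6. Shared causes, with no mediated effect.** Let metformin shift adiposity change by a (in SD, negative for loss), and let a shared cause give a within-arm correlation ρ between adiposity change and outcome. The adjusted coefficient is 1.33 - a·ρ·1.85.

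- ρ = -0.3, a = -0.2: 1.33 - 0.111 = 1.22
- ρ = -0.3, a = -0.5: 1.33 - 0.278 = 1.05
- ρ = +0.3, same shifts: 1.44 and 1.61
- a = 0: 1.33, no bias

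The true effect is 1.33 throughout. Shifts and correlations are assumed.

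**The case against.** The best defence is that the distortion may be small or absent. The group's own 85-adolescent trial found no significant overall difference in weight loss between metformin and placebo. In two of the cited trials BMI SDS fell while minimal-model insulin sensitivity, this trial's own measure, did not change. The girls in the premature pubarche trials were not obese, and the protocol itself criticises the design of those trials. If metformin does not move adiposity, the adjustment is harmless and can gain precision. This stands, but it concerns size. The plan cannot know beforehand which case holds and has no other between-group analysis to fall back on.

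Three narrower points also have force.
- Diet and activity, the shared causes named here, would be expected to produce a negative correlation and so understate the effect. No mechanism is offered for the +0.3 case, so overstatement is only a formal possibility.
- In the 6-month repeat the outcome runs beyond two years, and the plan does not say whether the covariates are redefined to match. They are post-randomisation either way.
- One sentence serves both aims and the words introducing the list are illustrative, so this may be Aim 1 wording carried over. As written, however, the named covariates go into each model.

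**Conclusion.** The concern holds. Followed as written, the plan tests Hypothesis 2 only through a coefficient conditional on two post-randomisation variables, one of them a body-composition change that Aim 2b treats as an outcome. That coefficient does not estimate the total effect of assignment to metformin unless metformin leaves adiposity change unaffected.

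The mismatch between question and analysis follows from the text alone and needs no numerical assumption. Its numerical size is unknown. Under the assumed mediated shares of 10% to 50%, the adjusted target falls from 1.33 to between 1.20 and 0.67. Under the assumed negative shared-cause correlation of -0.3 it falls to between 1.22 and 1.05 with no mediation at all. With no effect of metformin on adiposity there is no bias.

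This should be corrected before analysis, because it affects every planned between-group test of the randomised comparison. The finding is limited to Aim 2. Aim 1 is not randomised, and adjustment there is a different question.

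**What to change.** In the primary Aim 2 regressions, at end of treatment and at 6 months post-treatment, remove 2-year change in percent body fat and 2-year change in BMI. Adjust only for variables fixed before randomisation: sex, the baseline value of the outcome, and the two stratification factors (first-degree family history of T2DM and BMI stratum). Removing the two change scores is what cures the problem. The baseline outcome and stratification factors are suggested as suitable pre-randomisation replacements.

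Keep the models with BMI and body-fat change as secondary explanatory (mediation) analyses, labelled as such. State their assumptions, in particular that adiposity change and outcome share no unmeasured causes, and the time window of the covariates in the 6-month model. For Aim 1, results with and without the change covariates could be shown, but this is optional.

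The cost is a change of analysis wording. No data, visits or participants are added, and the models now planned are still run.

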We will recruit obese and normal weight subjects who are in early puberty as determined by Tanner staging of breast development and pubic hair in girls and by Tanner staging of pubic hair and estimation of testicular size in the boys. Adolescents whose pubertal status is at least Tanner II (T2), but no more than Tanner III (T3) will be asked to participate. In two studies that assessed insulin sensitivity across all stages of puberty, it was already significantly decreased from prepubertal insulin sensitivity at T2 and, while it had not yet completely recovered in early T5, it was still significantly increased from T4 insulin sensitivity (11;16). We will recruit through our metabolic syndrome and Good Life clinics, through advertisements, and from local pediatric clinics, including Denver Health Medical Center. Because of the ethnic make-up of our clinics, there will be Spanish-speaking only participants included in the study. The study coordinator is a native Spanish-speaker and, therefore, has the ability to consent the participants in Spanish using our consent and HIPAA forms that have been translated into Spanish. Lifestyle intervention materials are also available in Spanish. When the study coordinator is not available, an official Spanish interpreter will be used for the consent process and all study visits. Because of the anticipated high screen-failure rates due to failure to meet physical examination criteria (most notable Tanner staging criteria and BMI criteria), we will need to consent at least 40% more participants than we ultimately intend to enroll. Therefore, we anticipate that 225 participants will need to be consented for screening to be able to enroll 156 participants. The timeline of our experimental approach is shown below (Fig 2). A fasting baseline screening visit, to be performed at the pediatric Clinical Translational Research Center (CTRC), will include assessment of obesity status as determined by height, weight, BMI, waist circumference and hip circumference. An OGTT will be performed in all obese subjects to rule out IGT, IFG and diabetes in all subjects. The following screening labs will also be performed to examine for any significant underlying illness: AST, ALT, electrolytes, CBC, BUN, creatinine, lipids, and urinalysis.

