In adolescence, the number of routine visits to the pediatrician tends to drop. Therefore, we foresee a potential difficulty in recruiting children who are just starting puberty. For this reason, we are including children who are both Tanner 2 and Tanner 3 at study entry. In both of these stages of puberty, insulin sensitivity has been shown to be significantly decreased when compared with Tanner 1 and Tanner 5. The length of time required for progression through puberty varies in individuals. It is important to measure the post-treatment insulin sensitivity in Tanner stage 5, because insulin sensitivity in Tanner 4 may not be significantly different from earlier in puberty and only at T5 insulin sensitivity returns to its pre-pubertal level. For this reason, if a subject has not reached Tanner 5 in two years, they will not have their Study Visit 3 until Tanner 5 has been attained. This means that some subjects may need to be treated for a longer period of time. However, in order to compare differences in insulin sensitivity after treatment is stopped between subjects, the interval from treatment stop (Study Visit 2) to post-treatment follow-up (Study Visit 3), should be consistent.

The natural recovery of pubertal insulin sensitivity may confound measurement of metformin effects on insulin sensitivity as puberty progresses. In order to control for this, we have included a placebo-controlled group and a group of normal weight controls. This will allow us to compare changes in insulin

sensitivity from baseline to the end of puberty between obese treated subjects and both normal-weight and obese subjects who have not been treated.

The length of this study and potential difficulty with attrition are also limitations of this study. To limit the number of participants lost to follow-up, we will maintain frequent contact with participants with quarterly visits for anthropometric measurements, monthly visits for pill-counts and phone contact at least once between these visits. In addition to these visits, the participants in the treatment group will be contacted by telephone at least monthly to inquire about medication side effects and to review changes in diet and exercise. Due to our involvement in the TODAY study and other trials of metformin, our staff are experienced with working on long-term projects with obese and T2DM adolescents, with excellent study retention out as far as four years.

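### The supplementary estimate of maintenance after stopping metformin has no placebo contrast, so it mixes loss of drug effect with any natural change after Tanner V

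*Combined protocol and SAP*

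**What the plan says.** The Statistical analysis paragraph of section D plans two post-treatment analyses.

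- **Test of persistence.** Its purpose is given as "In order to determine if the benefit of treatment persists beyond stopping treatment", and the method is that "the above analysis will be repeated on the change from baseline to 6 months post-treatment for the obese treated and obese control groups only". The analysis being repeated is the linear regression comparing treated with untreated obese participants, so this is a concurrent placebo-controlled comparison.
- **Maintenance estimate.** "The mean change in each outcome from treatment stoppage to 6 months post treatment will also be calculated with 95% confidence intervals", and the stated purpose is "in order to assess maintenance of the level of each outcome". No contrast between arms is mentioned, and the text does not say whether the mean is taken within each arm or over both. On interpretation the plan is candid: "Although we are not powered for equivalence (to test the hypothesis that the 6-month change is equal to zero"), and the reader is to judge from the interval "the precision of the estimate and whether the difference is" clinically important. No numerical margin is given.

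Three other places bear on the second estimate. The Approach under Specific Aim 1 has obese participants stop study medication at the visit when Tanner V is reached. The same Approach, citing two studies of insulin sensitivity across puberty, reports that "while it had not yet completely recovered in early T5, it was still significantly increased from T4 insulin sensitivity". Potential Difficulties and Limitations/Alternatives warns that "The natural recovery of pubertal insulin sensitivity may confound measurement of metformin effects on insulin sensitivity as puberty progresses" and names the placebo and normal-weight groups as the control for this. It describes that control for the period from baseline to the end of puberty.

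**The concern.** The 6 months off drug start at Tanner V, when sensitivity may not have finished recovering. Over those months the metformin arm's mean change is the effect lost on withdrawal plus whatever change would have happened anyway. If sensitivity is still rising, the rise offsets the loss and the arm looks stable. If it is drifting down, an effect that is fully kept looks partly lost. The placebo arm was included to separate these two components, and the maintenance estimate makes no stated use of it. If the mean is pooled over both obese arms, the withdrawal effect is also diluted by participants who had no drug to withdraw.

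Sustained improvement after metformin stops is part of the study's stated hypotheses, so how much effect is lost or kept is a question readers will ask. This is the only planned estimate that looks directly at the interval after stopping.

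**Working it through.** **Inputs from the Sample size calculation paragraph.** SD of change 1.85; expected two-year changes 1.16 (metformin), −0.17 (obese control) and 1.6 (normal weight); 30 per group analysed. Units throughout are min⁻¹ per µU/ml × 10⁻⁴.

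**The plan's own figure.** One-way ANOVA, three groups of 30, two-sided 0.05. The grand mean is 0.863 and the sum of squared deviations is 1.698, so the noncentrality is 30 × 1.698 / 1.85² = 14.9 on 2 and 87 degrees of freedom. Power is 93.5%, against 93% stated. The inputs are therefore read as the plan used them.

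**Assumptions, because the documents give no figure for the 6 months after stopping.**
- SD of the stop-to-6-month change: 1.85 (1.0 is shown as a lower value).
- Drug effect at stopping: 1.16 − (−0.17) = 1.33.
- Natural change *r* over the 6 months, equal in both arms: 0 to 0.4. The value 0 is close to the plan's obese-control figure (−0.17 / 4 = −0.04 per 6 months). The value 0.4 is one quarter of the normal-weight two-year rise (1.6 / 4).

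**Expected values**, with *f* the fraction of drug effect lost:
- metformin arm alone: −1.33*f* + *r*
- placebo arm alone: *r*
- both arms pooled, equal numbers: −0.665*f* + *r*
- metformin minus placebo: −1.33*f*, whatever *r* is

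**95% half-widths at 30 per arm.**
- Within arm: 2.045 × 1.85 / √30 = 0.69 (0.37 if SD is 1.0).
- Between arms: 2.002 × 1.85 × √(2/30) = 0.96 (0.52 if SD is 1.0).

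**Intervals centred on the expected values:**

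| True loss | *r* | Metformin arm alone | Metformin minus placebo |
|---|---|---|---|
| 0.665 (half) | 0 | −0.67 (−1.36 to 0.03) | −0.67 (−1.62 to 0.29) |
| 0.665 (half) | 0.4 | −0.27 (−0.96 to 0.43) | −0.67 (−1.62 to 0.29) |
| 1.00 (three quarters) | 0 | −1.00 (−1.69 to −0.31) | −1.00 (−1.95 to −0.04) |
| 1.00 (three quarters) | 0.4 | −0.60 (−1.29 to 0.09) | −1.00 (−1.95 to −0.04) |

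With *r* = 0.4 the single-arm estimate understates the loss by 0.4, which is 60% of a half loss (0.4 / 0.665) and 40% of a three-quarters loss (0.4 / 1.00). The probability that the single-arm interval covers zero rises from 52% to 88% for half loss, and from 19% to 60% for three quarters. With *r* = 0 there is no bias.

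**The same mechanism in the persistence test.** The remaining between-arm difference is 1.33(1 − *f*), and *r* cancels. After complete loss it is 0, so the test would indicate a difference only at its 5% two-sided error rate. After half loss the remaining 0.665 would be detected with about 28% power (30 per arm, SD 1.85, unadjusted).

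**The case against.** The strongest reply is that persistence is decided elsewhere. The sentence before the maintenance estimate sets up a placebo-controlled regression for that purpose, and natural recovery common to both arms cancels in it. This stands. A reader might infer that the plan judges sustained benefit from the metformin arm's own change, so that a lost effect would be declared maintained. The documents do not support that. The mean change is an addition, its stated object is the level of each outcome, and no rule equates an interval covering zero with maintenance. The plan says that it is not powered for equivalence, and an interval such as −0.96 to 0.43 is plainly too wide to establish maintenance.

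The size of any bias is also open. The 0.4 comes from normal-weight adolescents before Tanner V. The plan's obese-control figure implies almost no natural change, Hypothesis 1 is that obese adolescents do not recover, and the limitations section says sensitivity is back to its pre-pubertal level at Tanner V. This stands as a limit on magnitude. It does not show that the bias is absent: the −0.17 is a 3-month placebo change in adult women, and the Rationale for Specific Aim 1 calls recovery in obese adolescents unclear.

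It can also be said that subtracting the two planned between-arm differences, at stopping and at 6 months, yields the missing contrast. In the same completers and without covariates this is exact. It comes without a confidence interval, however, and the covariates in the regressions make it approximate. Those covariates include post-baseline change in BMI and body fat, which may absorb part of a drug effect.

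Finally, the half-loss interval includes zero with no natural rise, and also under the between-arm contrast. That is imprecision, which the contrast does not cure.

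**Conclusion.** The concern holds for the supplementary estimate only. As written, the mean change from treatment stop to 6 months has no between-arm contrast, does not specify by-arm or pooled calculation, and cannot separate withdrawal loss from natural change, a confounder that the protocol itself names. The test of persistence is not affected by natural change that is equal in the two arms.

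The bias equals the natural change over the 6 months, and the documents give neither its size nor its direction in obese adolescents. It is 0 if there is none, an understatement of the loss by 0.4 under the assumed rise, and an overstatement if sensitivity falls. The between-arm contrast is free of this bias provided that natural change is the same in both arms, which randomisation supports among those followed to the last visit. The half-widths rest on an SD of 1.85 carried over to a 6-month change and on the plan's 30 per arm.

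**What to change.** In the Statistical analysis paragraph, add the metformin-minus-placebo difference in change from treatment stop to 6 months post-treatment, with its 95% CI, for each outcome. Name it as the estimate of how much treatment effect is lost or kept after stopping, and state its covariates. Say that mean changes are reported separately by arm, as description, and that no statement of maintained drug benefit will rest on the metformin arm's change alone. The placebo-controlled persistence regression stays as the test of whether a difference remains.

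The cost is a sentence or two of text. Both randomised obese arms are already due an IVGTT at treatment stop and 6 months later, so no visit or measurement is added. The price is precision: half-width about 0.96 instead of 0.69 at 30 per arm with SD 1.85. The contrast would detect complete loss of 1.33 with about 78% power and half loss with about 28%, so it should be presented as an estimate with its interval and not as proof of maintenance.
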